6.4 STUDY INTERVENTION/EXPERIMENTAL MANIPULATION ADHERENCE

Adherence to the study intervention will be monitored using multiple sources of information. These include (1) the frequency of messages sent and received using the Companion, which will be tracked weekly (2) attendance in the personal training sessions, which will be tracked weekly, and (3) outcome assessment attendance, which will be tracked at the end of the study.

6.5 CONCOMITANT THERAPY

6.5.1 RESCUE THERAPY

NA

7 STUDY INTERVENTION/EXPERIMENTAL MANIPULATION DISCONTINUATION AND PARTICIPANT DISCONTINUATION/WITHDRAWAL

7.1 DISCONTINUATION OF STUDY INTERVENTION/EXPERIMENTAL MANIPULATION

The criteria for discontinuing the intervention include the participant's request, as well as any life-threatening or potentially disabling event, including acute illness, an injurious non-accidental fall, or

hospitalization. These adverse events will be recorded in accordance with the Northeastern IRB requirements.

7.2 PARTICIPANT DISCONTINUATION/WITHDRAWAL FROM THE STUDY

The criteria for discontinuing the intervention include the participant's request, as well as any life-threatening or potentially disabling event, including acute illness, an injurious non-accidental fall, or hospitalization. These adverse events will be recorded in accordance with the Northeastern IRB requirements.

Additionally, an investigator may discontinue a participant if:

- Lost-to-follow up; unable to contact subject.
- The participant meets an exclusion criterion (either newly developed or not previously recognized) that precludes further study participation

The reason for participant discontinuation or withdrawal from the study will be recorded.

Subjects who sign the informed consent form and are randomized but do not receive the study intervention may be replaced. Subjects who sign the informed consent form, are randomized and receive the study intervention, and subsequently withdraw or are discontinued from the study, will not be replaced.

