5.2 EXCLUSION CRITERIA

1. Engage in structured physical activity for more than 2 days/week lasting 30 min/session-
2. Regularly use any assistive device for walking.
3. Likely to alter medications pertaining to cardiovascular or metabolic health

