9.4 STATISTICAL ANALYSES

9.4.1 GENERAL APPROACH

Descriptive statistics, for all normally distributed continuous data will be presented as means with standard deviations. Hypothesis testing will entail an intent-to-treat two-tailed design with a nominal type I error of 0.05. All participants will be included in the intent-to-treat analyses according to randomization regardless of their subsequent status. Missing data due to losses to follow-up will be

assumed to be at random. Random intercept mixed linear models that account for repeated measures will be used to compare primary and exploratory outcomes measured at various timepoints during the study. Models will be adjusted for covariates and the baseline value of the outcome variable where necessary.

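### Section 7.2 does not separate stopping the intervention from leaving the study, so outcomes needed for the intention-to-treat analysis can be lost after illness, a fall, hospitalization or a newly met exclusion criterion

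*Combined protocol and SAP*

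**What the plan says.** Section 7.1 deals with stopping the intervention: "The criteria for discontinuing the intervention include the participant's request, as well as any life-threatening or potentially disabling event", with acute illness, certain falls and hospitalization as examples. The next section is headed "7.2 PARTICIPANT DISCONTINUATION/WITHDRAWAL FROM THE STUDY". Its opening sentence is the same one, again ending "as well as any life-threatening or potentially disabling event, including acute illness, an injurious non-accidental fall, or hospitalization".

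Section 7.2 then continues: "Additionally, an investigator may discontinue a participant if" one of two conditions applies. The first is loss to follow-up. The second is: "The participant meets an exclusion criterion (either newly developed or not previously recognized) that precludes further study participation". The section closes by requiring a recorded reason for discontinuation or withdrawal, and by ruling out replacement of treated participants who later withdraw or are discontinued from the study.

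The exclusion criteria in Section 5.2 include "Engage in structured physical activity for more than 2 days/week lasting 30 min/session" and "Regularly use any assistive device for walking". A third concerns a likely change in cardiovascular or metabolic medication.

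Section 9.3 takes everyone randomized as the analysis population. Section 9.4.1 adds: "All participants will be included in the intent-to-treat analyses according to randomization regardless of their subsequent status". It assumes that data missing through loss to follow-up are missing at random. Section 9.4.2 plans multiple imputation as a sensitivity analysis, limited to outcomes missing through random causes.

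**The concern.** Stopping an intervention and leaving a study are different events. An intention-to-treat analysis depends on the difference, because a participant who stops the intervention can still be measured. Here both events share one list of grounds, and nothing says that measurement continues after either.

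The grounds are not neutral to the primary outcome, which is activity and sedentary time over one week at baseline and weeks 16 and 24. Someone who has been hospitalized, has fallen or has started to use a walking aid probably moves less. Someone who newly meets the structured-activity criterion probably moves more.

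The losses could also differ by arm. Coaches and participants are unblinded (Section 6.3). Treatment participants may be messaged 4 to 7 times a day and their wrist data upload passively, while control wrist sensors do not transmit (Section 8.1). Both arms see a trainer twice a week, but staff have more occasions to learn of an illness or of extra activity in the treatment arm. This makes differential loss plausible. The documents do not show that it will occur.

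**Working it through.** **1. Sections 7.1 and 7.2 side by side.** The shared sentence is identical and in both places names the intervention. In 7.2 it stands under a heading about the study, is followed by a further list of reasons to discontinue a participant, and leads to a statement about people discontinued from the study. Staff could reasonably take a hospitalization as study exit. They could also take it as stopping the intervention only. No sentence decides between the two.

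**2. The exclusion-criterion ground.** Section 6.1.1 gives all participants two supervised sessions a week of about 45 to 60 minutes, plus a plan for the other days. One own-time structured session of sufficient length makes 2 + 1 = 3 days, which exceeds the limit of 2 in Section 5.2. A participant in either arm can therefore come to meet that criterion by following the programme. The walking-aid and medication criteria can also arise during the study. Section 7.2 limits the ground to criteria that preclude participation but does not say which those are.

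**3. What the analysis plan covers.** A mixed model under missing-at-random in effect predicts an unmeasured participant from measured participants in the same arm with similar earlier values. Someone removed after a fall is then predicted as though the fall had not happened, unless the fall is reflected in the model. The covariates are not named. The imputation analysis is confined to randomly missing values, and no missing-not-at-random analysis is planned.

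**4. Room for losses.** The plan's required sample of 39 (Section 9.2) can be reproduced with a between-groups repeated-measures test, reading the stated 0.5 as Cohen's f: noncentrality = N·m·f²/(1 + (m − 1)ρ), with 1 and N − 2 degrees of freedom. With N = 39, m = 3, f = 0.5 and ρ = 0.5 this is 39 × 3 × 0.25 / 2 = 14.6. At alpha 0.01 the power is 0.859; at N = 38 it is 0.847, so 39 is the smallest N that reaches 0.85. Section 9.2 labels the 0.5 differently and bases it on HbA1c, so this is only a yardstick. Recruiting 46 leaves 46 − 39 = 7 spare, or 7/46 = 15.2%. On the same formula power is 0.922 at 46, 0.821 at 36 and 0.790 at 34. A handful of losses costs some power; the larger issue is bias.

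**5. When bias arises.** The documents give no event rates, so the inputs here are assumptions. Let the effect without events be 0.5 SD, let events occur with probability p_C (control) and p_T (treatment), and let an event worsen the outcome by k SD. If everyone is measured, the expected difference is 0.5 − k(p_T − p_C). If those with events are not measured, it is 0.5. The bias is k(p_T − p_C).

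| p_C | p_T | Expected lost of 46 | Bias, k = 0.5 | Bias, k = 1 |
|---|---|---|---|---|
| 10% | 10% | 23 × 0.20 = 4.6 | 0 | 0 |
| 5% | 15% | 23 × 0.20 = 4.6 | 0.5 × 0.10 = 0.05 | 1 × 0.10 = 0.10 |
| 5% | 25% | 23 × 0.30 = 6.9 | 0.5 × 0.20 = 0.10 | 1 × 0.20 = 0.20 |

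A simulation of 400,000 participants with a baseline-adjusted model agrees: −0.001 and −0.001; 0.051 and 0.101; 0.100 and 0.202 SD. The bias favours treatment here only because the treatment arm was given more harmful events. It reverses if control has more of them, or if the people removed are the more active ones.

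**The case against.** A reader might infer that 7.2 requires withdrawal from the study after illness, a fall or hospitalization. The text does not go that far. The repeated sentence speaks of the intervention, study exit is inferred from the heading and the surrounding lines, and no section says that measurement stops. The loss is a risk left open by silence.

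A reader might also infer that the programme disqualifies its own adherent participants. That is not supported either. The ground is discretionary and limited to criteria that preclude participation. The structured-activity criterion reads as an entry screen, and the prescribed exercise is given to both arms, so this route starts equally in each. What stands is that no sentence exempts trial-prescribed exercise.

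It can fairly be said that the intention-to-treat statement defines who is analysed, not who is measured; that mixed models keep people with partial data; and that Section 7.3 requires missed measurements to be rescheduled, with repeated contact attempts. This is right for people who miss a visit. It does not reach people whom the investigator has discontinued, for whom no visit may be sought.

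Finally, the measurement visits include repeated push-ups, squats and a 6-minute walk, so an investigator may have reason to omit some tests. That argues for discretion test by test. It does not argue against the week of passive activity monitoring that supplies the primary outcome.

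**Conclusion.** The concern holds as a gap in the plan. Section 7.2 duplicates 7.1, adds a discretionary ground that trial participation itself can bring about, and leaves outcome collection after discontinuation undefined. Read as placed, this is at odds with Sections 9.3 and 9.4.1, and the missing-data plan does not cover the losses that would follow.

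The size of the bias cannot be stated. It depends on event rates and effects by arm, which the documents do not give. The 0.05 to 0.20 SD in the table shows what assumed differences of 10 to 20 percentage points would do; with equal rates and equal effects the bias is about zero.

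A reader might try to size it from the feasibility study's reduction in sitting of about 2.1 h (126 min) a day: if 3 of 23 in one arm were lost and differed by that much, the mean of the remaining 20 would shift by 3/20 × 126 = 18.9 min/day. The documents do not support that use. The 3 of 23 is invented. The 126 min is a change over time in 6 people, not the gap between removed participants and their arm. The result is also a shift in one arm's raw mean, not a bias in the adjusted difference between arms.

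**What to change.** Reconcile Sections 5.2, 7.1, 7.2 and 9.4.1 with each other. The grounds for stopping the intervention remain the sponsor's decision and need not change for this purpose.

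Add a data-collection statement along these lines: participants who stop the intervention, or who later meet an exclusion criterion (including through exercise prescribed in the trial), are still invited to the scheduled outcome collection at Measurements 2 and 3, at minimum the 7-day activity monitoring, unless they withdraw consent or the investigator judges a given test unsuitable. Their data enter the intention-to-treat analysis in the arm to which they were randomized.

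Removal of the treatment arm's data hubs at dropout need not prevent this: the thigh monitor used in the three 7-day periods stores its data and is collected by staff (Section 8.1).

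The cost is a few sentences and some follow-up effort. The visits are already scheduled and may take place at home. Section 5.5 already provides for payment for all three measurements, up to $120 per participant. The change should be made early, because outcomes that were not collected cannot be recovered at analysis.

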7.3 LOST TO FOLLOW-UP

A participant will be considered lost to follow-up if he or she fails to return for both follow-up measurements and if study staff are unable to contact the participant after at least 3 attempts.

If a participant fails to be available for a follow-up:

- The researchers will attempt to contact the participant, reschedule the missed measurement with a week, counsel the participant on the importance of maintaining the measurement schedule and ascertain if the participant wishes to and/or should continue in the study
- Before a participant is deemed lost to follow-up, the investigator or designee will make every effort to regain contact with the participant (where possible, 3 telephone calls and, if necessary, a certified letter to the participant's last known mailing address or local equivalent methods). These contact attempts will be documented in the participant's study file.
- Should the participant continue to be unreachable, he or she will be considered to have withdrawn from the study with a primary reason of lost to follow-up

8 STUDY ASSESSMENTS AND PROCEDURES

8.1 ENDPOINT AND OTHER NON-SAFETY ASSESSMENTS

Table 1. Measures in Laboratory or Home

Measure	Measurement 1: Baseline (1-2 h)	Measurement 2: Follow-up 1 (4 months) (1-2 h)	Measurement 3: End of study (6 months) (1-2 h)
Heart rate and blood pressure	✓	✓	✓
Anthropometrics (Height, weight, waist, and hip circumference)	✓	✓	✓
Body composition (Bioelectrical impedance)	✓	✓	✓
Fasting blood glucose, and lipid profile	✓	✓	✓
Cognitive tests	✓	✓	✓
Physical function tasks	✓	✓	✓
Muscular and aerobic fitness	✓	✓	✓
Other			✓

The following tests and procedures will be conducted in the numbered order. All measurements will be made in a secure location to ensure privacy.

1. **Resting heart rate and blood pressure:** Heart rate and blood pressure will be measured using an automatically inflatable blood pressure arm cuff and monitor. These measures will be conducted in triplicate after a rest of 5 minutes between each measure.
2. **Anthropometrics:** Height and weight will be measured using a stadiometer and a standard digital weight scale, respectively, and circumferences will be measured by a trained research staff member using a measuring tape (in triplicate).
3. **Body composition:** Whole body percent fat and lean mass will be measured using Bioelectrical Impedance (BIA) and will be conducted by trained research staff. During the test, the participant will step bare feet on an electronic scale and hold handheld conduction electrodes. A weak electric current will flow through the body and the voltage is measured in order to calculate impedance of the body and thereby, the % of body fat and lean mass. The test will be completed within 30 s. The participant will not feel anything, and this test is similar to stepping on a weighing scale.
4. **Blood glucose and lipid profiles:** We will measure this using finger-stick blood analyses with a CardioChek Plus device (PTS Diagnostics). The CardioChek Plus is a certified fast, accurate and efficient portable analyzer capable of obtaining a full lipid profile and glucose readings in 90 seconds from a finger stick strip blood sample (15 – 40 micro Liters). The participant's blood will not be stored, as the finger stick analyses are immediate, and the measuring strips are discarded appropriately after the test.
5. **Cognitive tests:** The participant will complete a computer-administered test that measures various aspects of his or her cognitive abilities (attention, mental skills, memory, and processing speed).
6. **Physical function tasks:** The participants' pattern of walking (Gait), endurance, strength and balance will be evaluated by a series of performance assessments, which are safe and practical. These assessments mimic daily activities. Details of these performance assessments are as follows:
 - (i) **Gait:** the participant will be asked to walk at his or her usual pace on a 4-meter course twice. The researchers will time each of these walks with a stopwatch.
 - (ii) **Endurance:** the participant will first be asked to perform a series of chair stands. Beginning from a sitting position, the participant will be asked to stand up and then sit down five times in a row, as fast as he or she can, without using his or her arms to help.
 - (iii) **Strength:** the participant will be asked to squeeze a hand-held device to determine the maximum force he or she can produce with each hand repeating the test three times for the left and right hands.
 - (iv) **Balance:** the participant will first be asked to stand in different positions while keeping his or her balance first with eyes open and then with eyes closed. The tester will demonstrate what to do and will be nearby to steady the participant if he or she needs it.
7. **Muscular and Aerobic Fitness:** We will assess the participant's fitness with a series of short assessments explained below. A trained exercise physiologist will spot and supervise all exercises to ensure safety and proper technique. All testing procedures will be preceded with proper warm-up and instructions to minimize any risks. Details of these assessments are as follows:
 - (i) **Muscular endurance:** We will assess the endurance of the participant's lower and upper body by asking he or she to perform as many repetitions as possible. For the upper body we will do the Standard Push Up test where participants will perform as many pushups as possible. For the lower body we will use the Repetitive Squat Test where the participant stands with feet 15 cm apart, squats

until the thighs are parallel to the floor, and returns to an upright position. We will record the number of repetitions. The participant is free to terminate the tests at any moment either upon voluntary exhaustion or lack of desire to continue.

(ii) Aerobic Fitness- We will assess aerobic fitness using the 6-minute walk test. This is a simple test that requires no specialized equipment and only requires the participant to walk on a flat, hard surface for a period of 6 min. The total distance walked during this duration is measured using a measuring wheel.

8. Other: (i) 7-14 days after baseline, participants in the general exercise intervention group will have a virtual 30-min face-to-face counseling session with the researchers on: i) benefits of reducing sedentary behavior and increasing physical activity, and ii) various strategies to decrease workplace and home sedentary behaviors and initiate a physically active lifestyle.

(ii) Participants in the lifestyle physical activity intervention group will have a virtual 60-min face-to-face counseling session via a HIPAA complaint ZOOM session. This session will include the same components received by the general exercise intervention group supplemented with an additional 30-min of conversation to further personalize his or her physical activity prescription plan and create goals related to physical activity and sedentary behavior lifestyle choices. During this time the researcher will ask the participant in the lifestyle physical activity intervention group questions about his or her schedule, preferences, health-related behaviors, and other behaviors related to work schedule, hobbies/leisure interests, family dynamics, home and work environment, means of daily transportation, etc. that can be used to help support the participant towards achieving his or her physical activity and sedentary behavior lifestyle goals.

(iii) After study completion, participants will be asked to complete a follow-up interview in person during the end of study follow-up (month 6). The interview will take no longer than 15-20 minutes. The conversations may be recorded only with the participant's permission. Once the audio recordings are transcribed, the audio recordings will be immediately destroyed.

Table 2. Self-completed Measures (1 – 1.5 hours)

Measure	Baseline	Month 4 follow up	Month 6 follow up
General Health and Health Related Quality of Life	✓		
Perceived Competence Scale for Participating in	✓	✓	✓

Regular Physical Activity			
Short Health Care Climate Questionnaire	✓	✓	✓
Exercise Self-Regulation Questionnaire	✓	✓	✓
Basic Need Satisfaction in Relationships Scale	✓	✓	✓
Diet	✓	✓	✓
Activity Monitoring	✓	✓	✓

After completing the measurements in Table 1, participants will be given questionnaires and small activity monitors. It will take approximately 1-1.5 hours to complete the questionnaires. A research staff member will collect the questionnaires from the participant after a week.

1. Perceived Competence Scale for Participating in Regular Physical Activity: This is a 4-item questionnaire that assesses a participant's feelings of competence about engaging in physical activity.
2. Short Health Care Climate Questionnaire: This questionnaire has 6 items that assess a participant's perceptions of the degree to which the companion is supportive of autonomy; i.e., that the Companion considers the participants perspective and provides appropriate and meaningful feedback and opportunities for choice.
3. Exercise Self-Regulation Questionnaire: This is a 31- item self-report to measure the ability of the participant to regulate behavior to achieve one's goals
4. Basic Need Satisfaction in Relationships Scale: This scale addresses need satisfaction in general in one's life. It has 21 items assessing the three needs for competence, autonomy, and relatedness.
5. Diet: The participant will report frequency and portion size of foods consumed during the past month from a list of 70 commonly consumed food items on a questionnaire.
6. Activity Monitoring: physical activity measurement will be conducted in two ways. Firstly, using a thigh worn monitor. This measurement will be conducted for a period of 7-days at baseline and after 4 and 6 months. For this measurement the participant will wear 1 small lightweight (\approx 0.5 ounces) activity monitor (activPAL3TM, PAL Technologies, Glasgow, UK; product specs: <http://www.palt.com/pals/>) on his or her dominant thigh, which will be adhered to his or her skin using a hypoallergenic medical grade tape (3M TegadermTM Film, 3M, Minneapolis, MN; product specs: https://www.3m.com/3M/en_US/company-us/all-3m-products/~/3M-Tegaderm-Transparent-

Film-Dressing/?N=5002385+3293321979&preselect=3293786499&rt=rud). During the 7-day measurement periods, the participant will also complete a record of times the monitors were removed from his or her person. These thigh sensor data will not be transmitted wirelessly. The researchers will download the data from the devices upon collecting them from the participants. The researchers will go to the participant's office/home to collect these.

Secondly, during the entire duration of the study, including the three 7-day physical measurement periods with the thigh activity monitor, the participant will be asked to wear a small wrist sensor (~ 0.64 ounces) [(i). general exercise group: ActiGraph GT9X Link; (ii). lifestyle physical activity group: CentrePoint Insight Watch, Actigraph Corp. LLC, Pensacola, FL; product specs for GT9X available at <https://www.actigraphcorp.com/actigraph-link/> and for Insight Watch available at <https://www.actigraphcorp.com/cpiw/>). These devices will be worn on the non-dominant wrist on a watchstrap.

Participants in the general exercise intervention group will receive a new GT9X monitor every 1-4 weeks to ensure the devices always have enough battery life to measure physical activity. The researchers will go to the participant's preferred location (office or home) to provide a new sensor. These wrist sensor data will not be transmitted wirelessly. The researchers will download the data from the devices upon collecting them from the participants.

Participants in the lifestyle physical activity intervention group will receive an Insight watch that is capable of passively uploading motion data so that the researchers may get an understanding of his or her daily movement patterns. This information is confidential and will be used for research purposes only. No other data besides data about the participant's movement is gathered using any of the sensors. The researchers will come to the participant's office or home at the beginning of the study to install the data capturing systems (i.e., data transfer hubs). The decision on the location to install the hub (i.e., home vs office) will be determined in consultation with the participant. The location will be where the participant spends the most part of the week during the waking day. These data hubs are small devices that require a power source connection to communicate wirelessly with the device the participant will be wearing and relay data to the researcher. The researchers will uninstall the data hubs following completion of study participation either after the month 6 follow up or prior to that should the subject decide to drop out of the study. Please see the attached PDF detailing the data capturing and transmission process.

Participants in the lifestyle physical activity intervention group will also have the battery life of his or her wrist-worn activity monitor frequently monitored by the researchers via the passive data transfer system. When the researchers detect that the device has a low battery (battery life is approximately 2-3 weeks), the participant will be prompted to schedule a time to receive a new device from the researchers. The researcher will go to the participant's office or home to collect the monitor and return it charged by the next day to commence the daily physical activity measurement.

We will encourage participants in both groups to wear the sensors as much as possible so that: 1) we may be able to understand the differences in daily/weekly physical behavior change effects between the two intervention approaches, and 2) we may be able to tailor daily recommendations of participants in the lifestyle physical activity intervention group to maximize and maintain his or her gains and to help meet his or her goals. Participants may remove the sensors for brief intervals throughout the day (e.g., for showering). The researchers may provide participants in the lifestyle physical activity intervention group with retrospective feedback of his or her physical activity measurements via text-message frequently (4 to 7 times a day at intervals of 1 to 4 hours between 7

am – 10 pm), following the virtual session (Table 1 #8). To reiterate, daily retrospective feedback (health coaching) will last for 4 months, concluding at the month-4 follow up.

Change in outcome measurements will be provided to participants after the follow up at month 6, when requested by the participant.

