1.2 SCHEMA

1.3 SCHEDULE OF ACTIVITIES

	Pre-screening (Pre-consent)	Measurement 1 Day 1	Virtual visit Day 7-14	Measurement 2 Day 120-130	Measurement 3 Day 240-250
Review Eligibility	X				
Informed Consent		X			
Demographics		X			
Outcome Evaluation		X		X	X
Randomization		X			
Control & Experimental Interventions					►
Counselling			X		
Adverse Events Reporting		X	X	X	X

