6.3 MEASURES TO MINIMIZE BIAS: RANDOMIZATION AND BLINDING

1:1 Simple Randomization conducted by graduate assistant.

It has been suggested that blinding in behavioral interventions such as those involving physical activity and exercise is comparatively more challenging than in pharmacological or medical studies; this may be more relevant to pilot trials that are not conducted as part of a larger trial, which aim to assess the conceivable benefits of an intervention and the potential of conducting a future definitive RCT.⁷⁻⁹ While the health coaches and participants will not be blinded to treatment allocation, we minimize bias via the use of objectively measured outcome variables in both aims. Furthermore, the statistical analyst will be blinded to treatment allocation during analyses.

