10.1.1.1 CONSENT/ASSENT AND OTHER INFORMATIONAL DOCUMENTS PROVIDED TO PARTICIPANTS

Consent forms describing in detail the study intervention, study procedures, and risks will be given to the participant and written documentation of informed consent will be completed prior to starting the study intervention. The following consent materials are submitted with this protocol:

- Informed consent document
- Recruitment Flyer
- Recruitment Email template
- Recruitment quota reached email template

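### As scheduled, 6 or 7 of the 7 baseline days for the primary outcome fall after the randomisation day, and nothing in the available text withholds allocation until that week is complete

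*Combined protocol and SAP*

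**What the plan says.** In Section 1.3 a single column, "Measurement 1 Day 1", carries informed consent, outcome evaluation and "Randomization". Section 8.1, below Table 2, then says: "After completing the measurements in Table 1, participants will be given questionnaires and small activity monitors". The thigh monitor is worn for 7 days at baseline and again at each follow-up. Section 6.1.1 defines the primary outcomes from one week of accelerometry. No section names the primary device outright. Section 8.2 ties the primary outcome to taped sensors, and the thigh monitor is the one described as taped.

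On blinding, Section 6.3 states: "While the health coaches and participants will not be blinded to treatment allocation". It relies on objective outcome measures and a blinded analyst to limit bias. Sections 4.1 and 6.3 describe allocation only as 1:1 simple randomisation by a graduate assistant.

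Section 8.1 also requires a wrist sensor "during the entire duration of the study, including the three 7-day physical measurement periods with the thigh activity monitor". The general exercise group wears a GT9X Link, which does not transmit. The lifestyle physical activity group is the one that gets text feedback, so it is evidently the Companion arm. It "will receive an Insight watch that is capable of passively uploading motion data". Researchers visit that group's "office or home at the beginning of the study to install the data capturing systems", with no day number given. Section 10.1.1.1 adds: "Consent forms describing in detail the study intervention, study procedures, and risks will be given to the participant".

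Sections 9.4.1 and 9.4.2 specify random-intercept mixed models and leave adjustment for the baseline value to judgement.

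**The concern.** The hypothesis in Sections 4.1 and 9.1 is about greater improvement, so the baseline week is the reference for the treatment effect. A reference week should be free of anything that depends on allocation. Here unblinded participants may already know their arm, or know that their movement is being uploaded, while their baseline is recorded. An objective sensor records their behaviour faithfully, but it does not stop them from sitting less or walking more. A blinded analyst does not help with this either.

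If the Companion arm begins to improve in that week, the estimated effect at weeks 16 and 24 is too small. If the control arm becomes more active in that week, the estimate is too large. A shift common to both arms cancels.

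**Working it through.** **Day count.** Inputs: randomisation on Day 1 (Section 1.3); monitor issued after the Day 1 measurements and worn for 7 days (Section 8.1).

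- If Day 1 is the first wear day, wear covers Days 1-7, and 7 - 1 = 6 days follow the randomisation day.
- If Day 2 is the first wear day, wear covers Days 2-8, and all 7 days follow it.

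The order of events within Day 1 is not written, but it does not alter these counts.

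**Contact during the week.** Section 1.3 places the virtual counselling session on Day 7-14, and Section 8.1 places it 7-14 days after baseline.

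- A session on Day 7 would touch 1 wear day (wear 1-7) or 2 (wear 2-8).
- A session on Day 8 would touch 0 or 1.
- A session on Day 9 or later would touch none.

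Section 8.1 puts text feedback after that session. Section 6.1.1, however, refers to Companion communication in weeks 1 to 4 and supervised exercise in the first 16 weeks without defining day zero. If those weeks count from Day 1, Companion communication and up to two supervised sessions (2 x 45-60 = 90-120 min, both arms) fall in the baseline week. The communication would then conflict with Section 8.1.

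**Carry-over into the estimate.** Let s be the between-arm difference in the baseline week caused by knowledge of allocation or by remote monitoring. Let delta be the true arm difference at follow-up and rho the baseline-to-follow-up correlation, with equal SDs, so that the covariate slope equals rho.

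- Baseline as covariate: estimate = delta - rho x s.
- Change contrast, or baseline as one of the repeated outcomes with complete data: estimate = delta - s.
- Follow-ups compared with no baseline term: s does not enter, but precision is lost.

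**Illustration only.** The documents give no value for s or for rho in the activity outcomes. Assume s = 10 min/day of sitting and rho = 0.3 to 0.7.

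- Covariate: 0.3 x 10 = 3 to 0.7 x 10 = 7 min/day.
- Change contrast: 10 min/day.

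The only sitting figure in the documents is a reduction of about 2.1 h/day (126 min), from an uncontrolled feasibility test with n = 6 (Section 2.2). Against that, 3/126 = 2.4%, 7/126 = 5.6% and 10/126 = 7.9%. The sign may go either way.

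**The case against.** The strongest reply is that bias requires participants to know their arm during the wear week, and no passage says that they do. The time of disclosure is unwritten. The schema figure is not shown, the start of the intervention arrow in Section 1.3 is not legible, and the consent form is not available. A different watch reveals the arm only to someone who knows which model belongs to which arm. Remote monitoring needs the hub, whose installation day is not given. All of this stands, and it is why arm knowledge is called likely and not established. It does not remove the concern: following Section 8.1 as written means acting on the allocation before the baseline is complete.

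The reply also notes that the size is assumed. With 23 per arm, the standard error of an unadjusted mean difference is SD x sqrt(2/23) = 0.295 SD, so 10 min/day exceeds one standard error only if the SD is below 10/0.295, about 34 min/day. The documents give no SD. This too stands, although a systematic shift does not average out as sampling error does.

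Three stronger readings are tempting, and the documents support none of them:

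- *The baseline is demonstrably contaminated by a known amount.* Neither size nor direction can be derived.
- *The arms are measured with different devices for the primary outcome.* The thigh monitor, which appears to supply it, is the same in both arms and does not transmit. Only the wrist device differs.
- *Companion is already being delivered in the baseline week.* Section 8.1 places messages after the counselling session. Section 6.1.1 is ambiguous, which calls for reconciliation and does not prove overlap.

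**Conclusion.** The concern holds as an avoidable exposure of the primary baseline, not as a demonstrated bias. The count of 6 or 7 days out of 7 is firm for the available text. The rest depends on two inferences: that participants can recognise their arm in that week, and that the thigh monitor is the primary device. If an arm-specific shift occurs, it carries into both follow-up estimates at rho times its size (covariate) or in full (change contrast). Because baseline adjustment is left to judgement, which of these applies is not settled in advance. Confidence is medium. The change is worth making because it is cheap.

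**What to change.** 1. **Order of events (Sections 1.3 and 8.1).** Randomise, or at least disclose allocation and issue the arm-specific watch and hub, only after the 7-day baseline wear is complete. During that week everyone wears the non-transmitting GT9X already in the protocol. Merely writing down the present order would make the risk assessable but would not remove it.
2. **Model (Sections 9.4.1 and 9.4.2).** State that the baseline value is always a covariate and that the two follow-ups are the outcomes. Compared with a change contrast, this limits carry-over to rho times the shift and settles the choice in advance. It does not repair a shifted baseline.
3. **Timing statements.** Reconcile the communication weeks and supervised-exercise weeks in Section 6.1.1, the counselling session in Sections 1.3 and 8.1, and the text feedback in Section 8.1 with one another and with the baseline week. The schedule itself is for the investigators to set.

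Cost: no extra participants or outcome measurements. Arm-specific devices, and the booking of supervised sessions that are held on different days by group, start about one week later. Treatment-arm participants need a GT9X for a week. Hub installation may need its own visit if randomisation follows collection of the baseline monitor. If randomisation itself moves, people who leave during the baseline week are no longer randomised and so fall outside the intention-to-treat population. Delaying only disclosure avoids that.
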